8.5.2. Laboratory Data Beyond the Limits of Quantification

Quantitative laboratory measurements reported as “<X”, ie, below the lower limit of quantification (BLQ), or “>X”, ie, above the upper limit of quantification (ULQ), will be imputed as X for the purpose of quantitative summaries, but will be presented as recorded, ie, as “<X” or “>X” in the listings.

8.6. General Principles

Descriptive statistics (n, mean, standard deviation, median, 1st quartile, 3rd quartile, minimum, and maximum) will be calculated for continuous data as appropriate.

Categorical data will be summarized using counts and percentages. Missing values may be presented as a separate category when appropriate. Counts of zero in any category will be presented without percentage. Ninety-five percent (95%) confidence intervals (CIs) of the means or percentages may be calculated for selected continuous and categorical variables.

For time-to-event endpoints, Kaplan-Meier (KM) curves will be presented graphically by treatment group. KM estimates of cumulative incidence rates at specified time intervals (e.g., month 6, year 1, year 2, and yearly after randomization) and their 95% CIs will be presented. The hazard ratio and its corresponding 95% CI will be estimated from a Cox proportional hazard (PH) model with treatment group in the model. For between-group comparison, p-values (2-sided) will be calculated using log-rank tests.

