15.6. Primary Endpoint Analysis

The primary endpoint of this study is time to first occurrence of a confirmed (adjudicated) MACE, where MACE is defined as a composite primary efficacy endpoint that includes CV death, nonfatal MI, nonfatal stroke, or coronary revascularization.

The primary efficacy endpoint will be analyzed using Cox proportional hazards (PH) with treatment as a factor. The Cox PH will be performed using the FAS, with patients included in their randomized treatment group, regardless of the treatment they actually received. Note that the FAS includes patients who permanently discontinue treatment but remain in the study (patients are included regardless of their adherence to treatment). For this analysis, patients who are LTFU without experiencing a MACE will be censored at the time they are last known to be event-free. Patients who withdraw consent (withdraw from the study and refuse further contact) without experiencing a MACE will be censored at the time of consent withdrawal. Additionally, taking into account the period for CV event monitoring is every 3 months, when a patient who is LTFU or withdraws consent without experiencing a MACE is known to have later experienced a non-CV death, if the death was within 3 months of last contact, the patient will be censored at the time of death. If the death occurs more than 3 months after last contact, then the patient will be censored at the time of last contact. The hazards ratio (HR) and its 95% confidence interval (CI) and associated p-value will be provided.

In addition, Kaplan-Meier (K-M) curves will be provided, to provide a graphical description of the time to first occurrence of MACE.

Each individual component of the primary efficacy endpoint (CV death, nonfatal MI, nonfatal stroke, and coronary revascularization; each of the individual components are secondary time to event endpoints) will also be analyzed using Cox PH, to ensure consistency of the treatment effect across the components that comprise the composite endpoint. Each Cox PH will include treatment as a factor, and will be performed on the FAS with patients included in their randomized treatment group. The HR and its 95% CI will be provided for each individual component of the primary efficacy endpoint.

In addition, sensitivity analyses will be performed on the primary efficacy endpoint as needed. Additional details on the sensitivity analyses will be included in the SAP.

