3. STUDY ENDPOINTS

3.1. Primary Efficacy Endpoint

- Time to first occurrence of a MACE, where MACE is defined as the composite endpoint of CV death, nonfatal MI, nonfatal stroke, or coronary revascularization (MACE-4)

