7.2. Key Study Dates

7.2.1. Definition and Imputation of Key Event Dates

Date of End of Study (EOS): the study completion/early termination date recorded on the “Study Completion/Early Termination” CRF. Note that the patient may have a 30-day post EOS follow-up visit after this.

Date of Study Completion (DSC): For patients who did not complete the study, it is the later of a) the date of EOS and b) the date of the 30-day post EOS follow-up visit. For patients who completed the study, it is the latest date of a) the date of EOS, b) the date of the 30-day post EOS follow-up visit, or c) the date of death. This date is used to calculate the duration of study (follow-up) for each patient and all clinical events that happen during this period are adjudicated.

Date of First Dose of IMP (DFDOSE): for each patient, the DFDOSE is the date/time of administration recorded on the “On-Site Study Medication/ Compliance” CRF at Visit T1. If that field is missing, it is set to be next first date of administration at Visit T3.

Date of Last Dose of IMP (DLDOSE): the date of last dose is recorded on the End of Treatment CRF. In cases of missing either completely or partially, it is imputed as the earliest date of a) the last day of the month (if the month and year are present), or the last day of the year (if only the year is present); b) the Date of EOS; and c) the date of the last IMP dispense plus the number of tablets taken.

Date of Last Visit (DLVISIT): the last date recorded on either the *Visit Date* or the *Telephone Contact* CRFs. For patients who did not complete the study, this must be on or prior to the DSC.

Date of Last Known Alive (DALIVE): for patients whose vital status at the end of study is either alive or unknown, this is the last day when the patient is known to be alive. It is the latest “last known alive date” recorded on the *Survival Status* CRF. If this date is partially or completely missing, it is set to the later of last known alive date with imputation and DSC.

Date of Last Assessment for Non-Fatal Clinical Endpoints (DLASMT): Potential clinical endpoints are assessed every three months either in clinic or by telephone through the Post-EOS Phone visit. For patients who died during the study within 90 days of last visit, the DLASMT is set to the date of death. Otherwise, the DLASMT is set to be DLVISIT. Note that this definition also applies to new-onset diabetes mellitus (NODM) as an efficacy endpoint.

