7.2.5. Time to Event and Date of Censoring

For time-to-event analysis of clinical endpoint events (including new-onset type 2 diabetes), the start date is the date of randomization when the FAS is used, based on the ITT principle. When the PPS is used, the start date is set to be the date of first dose. For composite endpoints, the event date is the date of the first component event.

Patients who did not have any event in question will be considered as censored for the analysis. The date of censoring is determined as the following:

- Fatal events (CV death, fatal MI, fatal stroke, all-cause mortality): censored at Date of Last Survival Follow-Up.
- Non-fatal events and composite endpoints that include both fatal and non-fatal events: censored at the Date of Last Assessment.

Please see Section 18.3 for special censoring rule as applicable to patients from Ukraine as a result of the ongoing conflict.

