15.2.2. Primary Analysis Method of Primary Efficacy Endpoint

The null hypothesis, H_0 , is that there is no difference between bempedoic acid 180 mg/day and placebo in time to first occurrence of a confirmed (adjudicated) MACE. The alternative hypothesis, H_1 , is that bempedoic acid 180 mg/day is different from placebo:

$$H_0: \beta = 0 \text{ vs. } H_1: \beta \neq 0$$

Where the hazard $h(t)$ is modeled as: $h(t) = h_0(t)\exp(\beta x)$ and β is the log hazard ratio (HR).

The primary efficacy endpoint will be analyzed using Cox PH model with treatment as a factor. The HR and its 95% CI and p-value from log-rank test will be provided. In addition, KM curves will be provided, to present a graphical description of the time to first occurrence of confirmed adjudicated composite endpoint of CV death, nonfatal MI, or nonfatal stroke (4-component MACE).

If none of these 4-component MACE events is observed, the patient will be censored (Section 7.2.4).

The assumption of proportional hazard will be evaluated graphically for the primary efficacy endpoint by Schoenfeld residual plot and log-log plot. Ad hoc sensitivity analyses may be performed if needed.

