15.2.3. Primary Efficacy Endpoint Data Censoring Pattern

For patients who were censored, i.e., did not experience MACE-4 endpoint, the pattern of censoring will be summarized by treatment, including

- censored for non-CV death
- censored on or after completion of the EOS visit during closeout
- censored prior to the study closeout period and not by non-CV death
- censored within 30 days of the last dose
- censored more than 30 days after the last dose

The total patient-year lost-to-follow-up will be calculated by treatment group as the sum of time from the date of censoring prior to study closeout and not by non-CV death, to the May 15, 2022 when the study closeout was initiated.

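### Kaplan-Meier percentages labelled as cumulative incidence censor deaths outside the endpoint, so for most endpoints they modestly overstate absolute risk

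*SAP*

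**What the plan says.** SAP 8.6 sets the reporting rule for time-to-event endpoints: "KM estimates of cumulative incidence rates at specified time intervals" (month 6, year 1, year 2 and yearly after that), each with a 95% CI.

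The censoring rules are elsewhere:

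- SAP 3.1 builds the primary endpoint, MACE-4, from CV death, nonfatal MI, nonfatal stroke and coronary revascularization. Non-CV death is not in it, and SAP 15.2.3 lists patients "censored for non-CV death" as a censoring category.
- SAP 7.2.5: "Non-fatal events and composite endpoints that include both fatal and non-fatal events: censored at the Date of Last Assessment". SAP 7.2.1 fixes that date (DLASMT) for deaths: "For patients who died during the study within 90 days of last visit, the DLASMT is set to the date of death". For a later death it is the last visit. The patient is censored either way.
- SAP 7.2.5 for the fatal endpoints: "Fatal events (CV death, fatal MI, fatal stroke, all-cause mortality): censored at Date of Last Survival Follow-Up". A death from another cause is therefore censoring for CV death, fatal MI and fatal stroke.
- Protocol 15.6, for non-CV death after loss to follow-up or withdrawal: "if the death was within 3 months of last contact, the patient will be censored at the time of death". Otherwise censoring is at last contact.

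For the test and effect measure, SAP 15.2.2 says "The HR and its 95% CI and p-value from log-rank test will be provided", with the HR from a Cox model. SAP 15.5.4 adds events per 100 person-years and their difference for the primary and key secondary endpoints. No competing-risk estimator appears in the text available to me or in the SAP contents list. The text of SAP 15.4.4, 17 and 18 was not available, and their headings name no such analysis.

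**The concern.** A patient who has died cannot go on to have a first revascularization or stroke. Kaplan-Meier with that death censored assumes that the patient's later risk equals that of patients still in follow-up. One minus Kaplan-Meier then estimates risk in a hypothetical setting without deaths outside the endpoint. It exceeds the cumulative incidence, which is the proportion of patients who actually have the event by a given time, whenever such deaths occur while patients are still at risk.

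The SAP recognises the difference elsewhere. SAP 15.2.3 leaves non-CV deaths out of the patient-years lost to follow-up, and Appendix 6 stops imputing events at the date of non-CV death. For the same reason, the multiple-imputation and tipping-point analyses do not correct the percentages in SAP 8.6.

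At stake are the yearly absolute risks in the report, and any risk difference or number needed to treat that a reader derives from them.

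**Working it through.** **The plan's own figure.** The documents state no cumulative incidence to reproduce. The related design figure is 1620 events for at least 90% power at HR 0.85, two-sided alpha 0.05, 1:1. Schoenfeld's formula gives 4 × (1.960 + 1.282)² / (ln 0.85)² ≈ 1592 events and Freedman's gives 1599. With 1620 events, power is 90.5%. The design figure holds and does not depend on this point.

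**Inputs.**
- Placebo MACE-4 rate of 3.59% per year (SAP 8.1), used as a hazard λ = 0.0359.
- HR 0.85 (SAP 8.1), so the active hazard is 0.85 × 0.0359 = 0.0305.
- Times: 3.5 years, the planned average follow-up (SAP 8.1), and 5 years (Month 60, SAP Appendix 3).
- Non-CV death hazard δ: not in the documents. **Assumed** 0.5% to 3% per year, constant and equal in both arms.

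**Formulas, constant hazards.**
- One minus Kaplan-Meier: 1 − exp(−λt)
- Aalen-Johansen cumulative incidence: λ/(λ+δ) × [1 − exp(−(λ+δ)t)]

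Example, placebo, 5 years, δ = 0.01: Kaplan-Meier 1 − exp(−0.1795) = 16.43%; Aalen-Johansen 0.0359/0.0459 × [1 − exp(−0.2295)] = 16.04%. The excess is 0.39 points, or 2.4% relative.

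| Placebo MACE-4 | KM | AJ, δ 0.5% | AJ, δ 1% | AJ, δ 2% | AJ, δ 3% | Excess (points) |
|---|---|---|---|---|---|---|
| 3.5 years | 11.81% | 11.71% | 11.61% | 11.41% | 11.22% | 0.10 to 0.59 |
| 5 years | 16.43% | 16.23% | 16.04% | 15.66% | 15.29% | 0.20 to 1.14 |

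Relative excess: 0.9% to 5.2% at 3.5 years and 1.2% to 7.4% at 5 years.

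**Simulation check** (400,000 patients, δ = 1% per year, follow-up uniform on 2 to 4.75 years, 1% per year lost to follow-up). At 3.5 years Kaplan-Meier gave 11.85% and Aalen-Johansen 11.65%, a gap of 0.20 points, which matches the formulas.

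**Risk difference at 5 years.** Kaplan-Meier: 16.43% − 14.15% = 2.28 points. Aalen-Johansen: 16.23% − 13.98% = 2.25 points at δ = 0.5%, and 15.29% − 13.17%, which is 2.13 points before rounding, at δ = 3%. The implied number needed to treat is 1/0.0228 ≈ 44 against 1/0.0225 ≈ 44 to 1/0.0213 ≈ 47.

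**MACE-3**, assumed at half the MACE-4 rate (1.795% per year; SAP 8.1 expects at least 810 of 1620): excess 0.05 to 0.31 points at 3.5 years and 0.10 to 0.60 at 5 years.

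**A non-fatal endpoint**, assumed at 1% per year with death outside the endpoint assumed at 2% to 3% per year, 5 years: Kaplan-Meier 1 − exp(−0.05) = 4.88%; Aalen-Johansen 0.01/0.03 × [1 − exp(−0.15)] = 4.64% and 0.01/0.04 × [1 − exp(−0.20)] = 4.53%. The excess is 0.23 to 0.35 points, or 5% to 8% relative.

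**The case against.** The strongest reply is that the effect is small and that the reader gets other absolute measures. With about 7000 patients per arm, the 95% CI half-width for placebo MACE-4 at 3.5 years is at least 1.96 × √(0.1181 × 0.8819 / 7000) ≈ 0.76 points, against an excess of 0.20 points at 1% per year non-CV death. Five years lies beyond the planned average follow-up. The planned absolute contrast is the person-year rate difference in SAP 15.5.4, which does not have this bias, and the available text plans no Kaplan-Meier risk difference or number needed to treat. SAP 15.2.3 tabulates non-CV deaths by arm, SAP 15.2.1 counts first events by type, and SAP 3.2.2 includes a composite in which every death is an event.

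All of that stands as to size. It does not settle the label. The bias runs in one direction and does not shrink with sample size. The person-year rates cover only the primary and key secondary endpoints and do not give risk by year.

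Three stronger readings are tempting, and the documents support none of them:

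- *The treatment comparison is biased.* It is not. The Cox HR and log-rank test compare hazards of the endpoint event among patients still at risk, and censoring other deaths is the usual way to do that.
- *Benefit is misstated badly, or the number needed to treat comes out too high.* The risk difference moves by at most about 0.15 points at 5 years. An inflated difference makes the number needed to treat slightly too low.
- *Non-fatal components have the largest excess.* That holds only in relative terms. At 5 years, MACE-4 with 1.0% to 1.5% per year non-CV death is overstated by 0.39 to 0.58 points, against 0.23 to 0.35 in the non-fatal example.

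**Conclusion.** The point holds as a modest upward bias in reported absolute risks. SAP 3.1 to 3.2.2 list 1 + 6 + 10 = 17 time-to-event endpoints. It would be wrong to infer that all are affected: all-cause mortality and the composite with all-cause mortality leave no death outside the endpoint. The other 15 have some death outside the endpoint: non-CV death for the MACE composites; any death not counted for MI, stroke, revascularization, unstable angina and NODM; and death from other causes for the cause-specific deaths.

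For placebo MACE-4 the excess is a few tenths of a point at average follow-up and up to about one point at 5 years. These sizes rest on an assumed non-CV death rate, constant hazards and equal death rates in the arms; only the direction is certain. No test, HR, alpha, power figure or event target changes. This is a cheap improvement, not a threat to the trial's conclusion.

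**What to change.** In SAP 8.6, report cumulative incidence at each time point, with 95% CI, from the Aalen-Johansen estimator, with deaths outside the endpoint as competing events. Keep Kaplan-Meier for all-cause mortality and the all-cause-death composite. Kaplan-Meier plots may stay for the other endpoints if labelled as such. Leave the Cox and log-rank analyses as they are.

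The text also needs a rule for two groups in SAP 7.2.1: deaths more than 90 days after the last visit, which fall after DLASMT, and unadjudicated deaths found only by survival search. One rule that fits the existing censoring dates is to count a death as competing only if it falls on or before the endpoint's censoring date, keep later deaths censored, and tabulate their number by arm.

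The cost is a software option and a paragraph of SAP text. No new data are needed, and SAP 5.3 allows finalization up to database lock and unblinding. The downside is slightly lower reported percentages and less direct comparison with trials that report Kaplan-Meier.

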9. DISPOSITION OF STUDY PARTICIPANTS

All patients screened will be accounted for in this study. The primary reasons for screen failure are collected in the *Screen Failure* CRF and will be tabulated and listed. For screen failures due to inclusion or exclusion criteria, the unmet criterion will be presented in a listing. Patient disposition including withdrawals (both from study treatment and the study), and final survival status will be summarized for the FAS and listed. The number of patients in each analysis set will also be presented.

In addition, the disposition for patients in the FAS with baseline ezetimibe use will also be provided.

10. PROTOCOL DEVIATIONS

All protocol deviations (PDs) will be presented in a listing, including any relationship to the COVID-19 pandemic.

Major protocol deviations, and all protocol deviations related to COVID-19 will be summarized by treatment group and categories.

The protocol deviations are recorded and tracked in the Clinical Trial Monitoring System. The final protocol deviations will be determined before treatment groups are unblinded.

11. DEMOGRAPHIC AND BASELINE CHARACTERISTICS

Demographic data and other baseline characteristics will be summarized by treatment group for the FAS, SAS and PPS. These data will also be provided for patients in the SAS with baseline ezetimibe use. No statistical testing will be carried out for demographic or other baseline characteristics.

The following demographic and other baseline characteristics will be summarized and listed for this study:

- Age (years)
- Age category (<65 years, ≥65 to <75 years, or ≥75 years)
- Sex (female vs male, at birth)
- Race (American Indian or Alaska Native, Asian, Black or African American, Native Hawaiian or Other Pacific Islander, White, and Other)
- Ethnicity (Hispanic or Latino vs Not Hispanic or Latino)
- Region (defined in Section 7.5.1)
- Weight (kg)
- Height (cm)
- Body mass index (BMI) (kg/m^2) = $\text{weight (kg)}/\text{height (m)}^2$
- BMI category (<25 kg/m^2 , 25 to <30 kg/m^2 , or ≥30 kg/m^2).
- Baseline vital signs (systolic blood pressure, diastolic blood pressure, and heart rate)
- Baseline key laboratory Results (LDL-C, hs-CRP, Non-HDL-C, TC, HDL-C, and TG) (LDL-C results are presented in both conventional and standardized units, the others will be in conventional units only)
- Baseline LDL-C category (<130 mg/dL, ≥130 mg/dL and <160 mg/dL, ≥160 mg/dL)
- Baseline hs-CRP category (<2 mg/L, ≥2 mg/L)
- Baseline CVD risk category (Section 7.5.3), for patients with documented CVD history (secondary prevention), the prior history of CAD, PAD or CeVD.
- History of diabetes mellitus (Yes vs No, as collected in the *Targeted Cardiovascular History/Risk Factors* CRF)
- Baseline glycemic status (Section 7.4)
- History of hypertension (Yes vs No, Section 7.5.2)
- Alcohol consumption (Non-drinker, Former Drinker, or Current drinker)
- Tobacco use (Never used, Former user, or Current user)
- Baseline background lipid-modifying therapy (LMT) (Statin use including statin only or Statin + other LMT, other LMT without statin, or none, see also Section 7.6.1)

- Baseline statin intensity (none, very low, low, moderate, and high, see [Section 7.6.2](#) and [Appendix 5](#))
- Baseline ezetimibe use (Yes vs No)
- Statin intolerance criteria as collected on the *Statin Intolerance Criteria Compliance* CRF [REDACTED]
- Baseline estimated glomerular filtration rate (eGFR) category (≥ 90 mL/min/1.73m²; 60 to <90 mL/min/1.73m²; 30 to <60 mL/min/1.73m²; or <30 mL/min/1.73m²)
- History of chronic kidney disease history (Yes vs No, [Section 7.5.4](#))

12. MEDICAL AND SURGICAL HISTORY

General medical and surgical history information will be presented by Medical Dictionary for Regulatory Activities (MedDRA) SOC and PT for the FAS. Medical history conditions are those conditions that started prior to screening and collected on the *Medical History* CRF.

13. MEDICATIONS

13.1. Prior and Concomitant Medications

Prior and concomitant medications will be presented for the SAS. In general, the medications will be summarized by Anatomical Therapeutic Chemical (ATC) drug class (ATC level 4, anatomical or pharmacological groups), preferred names, and by treatment group.

According to the protocol, non-statin medications up to 3 months prior to screening are collected. All prior use of statins is collected on a separate *Prior and Concomitant Statin Therapy for Dyslipidemia* CRF with pre-defined terms. Therefore, prior use of statins will be presented separately from other prior medications.

13.2. Antidiabetic Medications

For patients with diabetes at baseline in the FAS, and the subset with inadequately control diabetes, baseline antidiabetic medications (see [Section 7.4.2](#)) will be summarized by preferred names and treatment group.

Patients who had a change to antidiabetic medications will be summarized by baseline glycemc status:

- within 12 weeks before screening through 12 months (365 days) post-randomization;
- within 12 weeks before screening to before randomization (only applicable for patients with diabetes at baseline);
- from randomization through 12 months (365 days) post-randomization.

13.3. Lipid-Modifying Therapy

The use of LMTs (Section 7.6.1) will be summarized separately by categories including pre-specified statins, and by treatment group for the FAS, including:

- Baseline LMT (Section 7.6.3)
- Baseline statin intensity (Section 7.6.2), shift to maximum intensity during the study, and shift to the statin intensity ongoing at the end of the study
- Cross-in LMT (Section 7.6.4), including a summary of the time to first cross-in LMT (censored at DLASMT if no cross-in).

